1.0 Research Introduction

1.1 Purpose/Specific Aims

This study (R33), which is being funded by the National Center for Complementary and Integrative Health (NCCIH), aims to evaluate the impact of a novel intervention, Mindfulness Oriented Recovery Enhancement (MORE), on opioid use and chronic pain among individuals receiving methadone maintenance treatment (MMT). The main goal of this study is conduct a clinical trial to assess online MORE, delivered remotely, through secure video or phone conferencing, with respect to a range of clinical outcomes. This study will involve a 2-arm individually randomized controlled trial design that compares MORE and treatment as usual (TAU).

A. Objectives

- Aim 1. Determine MORE's efficacy for increasing opioid abstinence relative to TAU.
- Aim 2. Determine MORE's efficacy for impacting secondary outcomes relative to TAU.
- Aim 3. Evaluate the degree to which MORE's impact on opioid use and pain are mediated by changes in the three core therapeutic mechanisms of MORE.
- Aim 4. Identify moderators of treatment response.

B. Hypotheses / Research Question(s)

As compared to the TAU group, the MORE group will 1) have a longer time until opioid relapse (primary outcome) and 2) have greater opioid abstinence, less other drug use, greater MMT adherence, and greater reductions in craving, pain symptoms, and emotional distress (secondary outcomes).

We hypothesize that the impact of MORE on opioid use and pain outcomes will be mediated by improvements in metacognitive awareness (mindfulness), negative emotion regulation (reappraisal), and amplification of natural reward processing (savoring).

Based on prior studies, we hypothesize that gender will moderate treatment response. ¹⁹⁻²¹ We will also explore other potential moderators like race, income, mental health, trauma, and MMT phase (i.e., stabilization/early recovery vs. maintenance/sustained abstinence).

1.2 Research Significance (Briefly describe the following in 500 words or less):

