All study participants will participate in three video, phone conferencing, or in-person visits at baseline, 8-, and 16-weeks. Information will be collected on demographic characteristics, substance use, methadone treatment, opioid craving and withdrawal, physical pain, non-reactivity, negative and positive affect, attentional bias, cognitive and

Version Number: 15, 2/2/2022 Protocol Number: Pro20190016877 PI Name: [name]

Protocol Title: Mindfulness Oriented Recovery Enhancement (MORE) as an Adjunct to Methadone Treatment RESERVED FOR IRB STAMP
DO NOT MODIFY THIS SPACE

mental health, physical health, and intervention implementation and attitudes. At the baseline and 8-week research visits, participants will complete three cognitive tasks on a computer or tablet that assess inhibitory control, implicit (automatic) associations, and the precedence of global features in visual perception. Urine and/or saliva samples will be requested at each assessment for confirmation of self-reported drug use or recent drug test results will be obtained from the participants' clinic chart. In addition, participants will partake in daily ecological momentary assessments (EMA) throughout the 16-weeks of study participation that include brief measures of pain intensity, mood, and substance use. Participants will also be asked to initiate communication via smartphone, computer, or tablet when they either lapse to opioid use or experience serious craving. Self-initiated responses will include information about the circumstances surrounding their craving/lapse. A synopsis of all study instruments are included below (see 1.98 – Study instruments).

C. Define the duration of the study and the length of time each subject will participate in the study. This study is expected to take two years. Each subject will participate in the study for a total of 16-weeks.

- **D.** Describe any primary and secondary study or safety endpoints
 - Primary Outcome: time until opioid relapse
 - Secondary Outcomes: opioid abstinence, days of drug use, MMT adherence, craving, pain symptoms, and emotional distress

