Hypothesis 1.1. (**Primary Outcome**) MORE will result in longer duration of time to first opioid lapse and MMT dropout than TAU. We will use survival analysis (Kaplan Meier curves and marginal model analysis for multivariate survival data)³⁴ to test effects of MORE vs. TAU on time until first opioid lapse and MMT dropout—evidenced either on EMA, Timeline Follow-Back, urinalysis or medical records (whichever is first). Survival analysis will be run once, at 16 weeks post-baseline. Clustering within cohort will be adjusted in the multivariate marginal model analysis.³⁴ We will estimate the hazard ratios of opioid lapse and MMT dropout when comparing MORE with TAU, controlling for covariates.

Hypotheses 1.2 and 1.3 (Secondary Outcomes). MORE will result in more days of opioid abstinence (or less days of use) and a higher rate of biochemically-verified abstinence over time than TAU. Generalized linear mixed model (GLMM)³⁵ repeated measures analysis will be used. Specifically, identity link will be used for "number of abstinent days" as the dependent variable, and logit link will be used for "opioid abstinence (yes/no via urinalysis)" as the dependent variable. Days of use/abstinence will be assessed via EMA, number of drug use days since last visit and past 30 days, and the Timeline Follow-Back. In cases of conflicting findings across data sources, we will assume the highest number of days of use or lowest number of abstinent days recorded for that period. Analyses will include group (MORE vs. TAU), time, and group by time interactions as the fixed effects independent variables. Correlations among repeated measures and among subjects within cohorts will be modeled using nested random effects. Potential confounders that meet the p<0.10 criterion stated above will be entered as covariates. Linear contrasts will be constructed to test between-group differences in "days of use" or "days of abstinence" separately at each timepoint. In comparing days of use, if a substantial proportion of subjects do not use opioids, resulting in excessive zero days of use, we will use a two-part logistic/linear analysis model.^{36,37}

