Hypotheses 1.4 (**Secondary Outcomes**). MORE will result in more days of MMT and greater decreases in pain severity, pain interference, days of non-opioid drug use, and emotional distress over time than TAU. We will use GLMM to compare days of MMT, pain severity and interference scores, days of non-opioid drug use, and emotional distress among the treatment groups, using the same analytic strategy described above.³⁵

AIM 2 Analyses. Mediational analysis. To test whether the three mediators specified in Aim 2 statistically mediate the effect of treatment on changes in days of opioid use over time, we will conduct a multivariate path analysis via a latent growth curve framework conducted in structural equation modeling software (i.e., MPlus) according to established guidelines³⁸ evaluating 3 regression paths for each mediator: A) 'a' path between treatment indicator and pre-post treatment change in the mediator (e.g., savoring); B) the 'b' path between pre-post treatment change in the mediator (e.g., savoring) and the latent slope (change) of the outcome (e.g., opioid use); and C) the 'c' path between treatment indicator and the latent slope of the outcome (e.g., opioid use). We will emulate similar multivariate analyses from published studies of meditation interventions^{39,40} by testing treatment effects on the latent slope of changes in days of drug use over time as mediated by changes in proposed mechanisms. We will test mediation by evaluating the significance of the joint product of the a and b paths, with bootstrapping used to test the significance of the indirect effect. A similar model will be estimated for changes in pain severity. Path models will be corrected for multiple comparisons. Simultaneous estimation of mediational effects from all three mediators to days of drug use and pain will allow us to determine unique effects of the core therapeutic mechanisms of MORE (mindfulness, reappraisal, savoring) – representing one of the most comprehensive mediation modeling attempts of the MORE intervention research program to date.

Version Number: 15, 2/2/2022 Protocol Number: Pro20190016877 PI Name: [name]

Protocol Title: Mindfulness Oriented Recovery Enhancement (MORE) as an Adjunct to Methadone Treatment RESERVED FOR IRB STAMP
DO NOT MODIFY THIS SPACE

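### The level for the lapse test is not stated consistently: Hypothesis 1.1 puts MMT dropout beside opioid lapse under the primary label with no success rule, and Holm does not exempt the primary

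*Combined protocol and SAP*

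**What the plan says.** In Section 6.1 A (Aim 1 Analyses), Hypothesis 1.1 carries the primary-outcome label and reads "MORE will result in longer duration of time to first opioid lapse and MMT dropout than TAU". The analysis follows suit: "We will estimate the hazard ratios of opioid lapse and MMT dropout when comparing MORE with TAU". No sentence says which result, or which combination of results, makes the primary hypothesis succeed.

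The opening paragraph of Section 6.1 A applies the Bonferroni-Holm procedure to the outcome analyses. It lists no family and does not set the primary apart. The path models and the EMA models have correction sentences of their own, so this general sentence most naturally covers the Aim 1 outcomes, primary included.

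Other sections name a single primary:

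- Section 1.3 D: "Primary Outcome: time until opioid relapse", followed by "Secondary Outcomes: opioid abstinence, days of drug use, MMT adherence, craving, pain symptoms, and emotional distress". Section 1.1 B makes the same split.
- Section 1.6 B labels only time to first opioid lapse as primary and lists time until MMT dropout as a separate, unlabelled item.
- Sections 1.5 and 6.1 B size the trial for a hazard ratio of 0.55 with 80% power at two-sided 5%. Section 6.1 B makes clear that this is relapse to opioid use. No effect size or event rate is given for MMT dropout.

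Hypothesis 1.4 already tests retention in treatment as a secondary outcome: "MORE will result in more days of MMT and greater decreases in pain severity, pain interference, days of non-opioid drug use, and emotional distress".

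**The concern.** The section that will be programmed from does not match the sections that define the primary. Taken together, they allow at least three rules for the same trial:

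1. Lapse alone, at two-sided 5%.
2. Lapse and dropout as a two-test Holm family, so that the smaller p-value must first pass 2.5%.
3. Both events required, which is a literal reading of the conjunction in Hypothesis 1.1.

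Suppose lapse gives p = 0.03 and dropout shows nothing. Rule 1 calls the trial positive; rules 2 and 3 call it negative. If the rule is chosen after the results are known, the nominal 5% no longer describes the primary test. If the stricter rule is applied, the trial is judged at a level for which it was not sized.

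**Working it through.** **Inputs.** Hazard ratio 0.55, two-sided 5%, 80% power, accrual 1.5 years plus 16 weeks (Sections 1.5 and 6.1 B); median time to relapse 99 days, arm not stated (6.1 B); up to 92 per group (1.5); 16 weeks of participation each (1.3 C). Relapse and lapse are treated as the same endpoint.

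**The plan's own figure.** Freedman's formula: events = (1.960 + 0.842)² × (1 + 0.55)² / (1 − 0.55)² = 7.849 × 2.4025 / 0.2025 = 93.1, rounded up to 94, which is 2 × 47. The stated 47 per group is matched by one endpoint at the full 5%, if every participant has an event. At a 2.5% first step the same formula needs 113 events, or 57 per group.

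**Power at the design point.** Schoenfeld's formula: events = 4 × 7.849 / (ln 0.55)² = 31.40 / 0.3574 = 87.8.

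Power = Φ(|ln 0.55| × √(d/4) − z). With d = 87.8 the first term is 0.598 × 4.686 = 2.802.

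- At 5%: Φ(2.802 − 1.960) = 80%.
- At 2.5%: Φ(2.802 − 2.241) = 71%.

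**Where the verdict depends on the reading.** The observed hazard ratio that just reaches a given level is exp(−2z/√d):

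- p = 0.05: exp(−3.920/9.372) = 0.658.
- p = 0.025: exp(−4.483/9.372) = 0.620.

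An observed lapse hazard ratio between about 0.62 and 0.66 passes at 5% and fails at 2.5%. Under Holm it is rescued only if dropout itself reaches p ≤ 0.025.

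**How often that happens.** The probability that 1.960 < |Z(lapse)| < 2.241 while |Z(dropout)| < 2.241, under a bivariate normal with lapse at 80% power, is 8.6 to 8.7% if dropout has no effect. If dropout is assumed also to have 80% power, it is 2.5 to 4.0% (correlation 0 to 0.7).

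**Power at 184 enrolled.** Exponential times, 92 per arm, no loss, no allowance for cohort clustering. The hazard is ln 2 / 99 in the arm that has the 99-day median, and the other arm's follows from the ratio 0.55. With 112 days of follow-up each, the event probability is 1 − exp(−112λ). With accrual R = 548 days and F = 112 days it is 1 − [exp(−λF) − exp(−λ(R + F))]/(λR).

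| Follow-up | Arm with 99-day median | Event probability, TAU / MORE | Events | Power at 5% | Power at 2.5% |
|---|---|---|---|---|---|
| 16 weeks each | TAU | 0.54 / 0.35 | 82 | 77% | 68% |
| 16 weeks each | MORE | 0.76 / 0.54 | 120 | 91% | 85% |
| To study end | TAU | 0.88 / 0.73 | 148 | 95% | 92% |
| To study end | MORE | 0.97 / 0.88 | 170 | 97% | 95% |

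The 2.5% step costs about 2 to 9 points. The study-end rows follow the sizing statement, although Section 1.3 C limits participation to 16 weeks.

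**The case against.** The strongest reply is that the primary is identifiable. Three sections name lapse or relapse alone, two of them list MMT adherence as secondary, the sizing uses one endpoint at 5%, and Hypothesis 1.1 uses its label in the singular. On that view dropout is only modelled alongside lapse in the multivariate survival model, and a single named primary involves no multiple comparison. This shows intent, and it is why the fix is small. It does not settle the text. The marginal model handles dependence between event times, but it supplies neither a success rule nor an alpha allocation, and the Holm sentence contains no exemption.

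The second reply is that little power is lost. That stands. None of the four scenarios at 184 enrolled moves from above 80% to below it because of the 2.5% step; the one below 80% is already at 77% at the full 5%, for reasons of follow-up.

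A reader might infer more than the documents support:

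- **That Holm runs over all of Hypotheses 1.1 to 1.4.** Counting nine outcomes gives a first step of 0.56% and lapse power of 51% at 88 events. The count is an assumption, and 51% is a floor that rises as other outcomes are rejected.
- **That joint power is 64 to 71%.** This needs an assumed 80% power for dropout, for which the documents give no input.
- **That the endpoint is a composite.** The phrase about whichever comes first follows a list of data sources, and two hazard ratios are then estimated.
- **That the interim look inflates alpha to 8.6%.** That requires stopping at p < 0.05, which does not fit Section 6.3 E's requirement of statistically overwhelming differences.

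**Conclusion.** The point holds as an inconsistency about the level and success rule of the primary test, and it should be corrected before any between-group analysis. The plan does not leave the primary unidentified: most sections point to lapse. Nor does it follow that the trial is underpowered because of Holm. What is unsettled is the verdict when the lapse p-value lies between 0.025 and 0.05 and dropout does not reach 0.025: positive under Sections 1.1, 1.3 and 1.6, negative under a two-event Holm or a both-events rule.

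The size is 80% against 71% lapse power at 88 events, and about 2 to 9 points at 184 enrolled. These figures assume exponential times, proportional hazards and no loss. They ignore the cohort clustering that Section 6.1 A says will be adjusted for, and the documents give no figure from which to allow for it.

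Minor and separate: Section 6.1 A says "Survival analysis will be run once, at 16 weeks post-baseline", while Section 6.3 E permits an optional look at 50% accrual with possible stopping. The criterion there has no number in these documents, and the DSMB's operating procedures are not among them. With a strict boundary such as two-sided p < 0.001 and a final test at 5%, overall alpha is 5.03% with 41% of events at the look. It cannot exceed 5% + 0.1% = 5.1% at any timing, so the effect is negligible. The 41% assumes uniform accrual and the 16-week cap; follow-up to study end gives 29 to 35%.

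**What to change.** In Hypothesis 1.1, state that time to first opioid lapse is the sole primary endpoint, tested at two-sided 5% outside the Holm procedure. Move time to MMT dropout to the secondary outcomes; its hazard ratio can still come from the same marginal model.

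In the opening paragraph of Section 6.1 A, restrict Holm to a listed secondary family with one prespecified test per outcome: time to MMT dropout, days of opioid abstinence or use, biochemically verified abstinence, days of MMT, pain severity, pain interference, days of non-opioid drug use, and emotional distress. Decide whether craving belongs: Sections 1.1 B and 1.3 D list it as secondary, but Hypotheses 1.2 to 1.4 do not. Make confirmatory secondary claims only if the primary is significant.

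Separately, reconcile the single-analysis sentence with Section 6.3 E. Either state that no between-group efficacy test is done at the 50% look, or give the boundary as a number and name the endpoint.

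The cost is wording only, with no added participants. MMT dropout loses its primary label, and confirmatory secondary claims come to depend on the primary result. That dependence is a design choice the sponsor should make knowingly; naming the sole primary and its level is enough to remove the conflict.

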1.5 Sample Size Justification

With 1.5 years of subject accrual and an additional follow-up of 16 weeks after the accrual interval, our study needs 47 subjects per group to test a hazard ratio of 0.55 when comparing MORE to TAU, with 80% power and alpha=5% (two-sided). To account for attrition, we will recruit up to 92 subjects per group (a total of 184 subjects at a 1:1 ratio for MORE vs. TAU).

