8	Discussion of how to maintain mindfulness practice; finding a sense of meaning and purpose of life; development of mindful recovery plan; imaginal rehearsal of skill learning; mindful breathing							

Treatment as Usual (TAU). In the MMT programs, clients typically come to the clinic regularly (usually 6 days per week at the beginning of treatment) to get their methadone dose; during periods of social distancing or as clients progress through the program and remain abstinent from drugs, they can "take home doses" that they can take on days that they are not required to come to the clinic. Timing of the initiation of take-home doses and the scheduling of clinic days varies across clinics. Clients see their clinic substance abuse counselor for individual

7

Version Number: 15, 2/2/2022 Protocol Number: Pro20190016877 PI Name: [name]

Protocol Title: Mindfulness Oriented Recovery Enhancement (MORE) as an Adjunct to Methadone Treatment RESERVED FOR IRB STAMP
DO NOT MODIFY THIS SPACE

counseling, usually weekly at the beginning of treatment, with decreasing frequency if they remain abstinent and progress through treatment. Depending on clients' stage of MMT and success with remaining abstinent from drugs, they may be required to attend clinic treatment groups. During periods of social distancing, these individual or group sessions may be remote, through video conference or phone. Also, some clients may choose to go to voluntary counseling, educational, or support groups (none of these groups involve coping with pain oriented or are mindfulness-based). All individual treatment characteristics, including methadone dosage, take-home dosing, clinic attendance and attendance at clinic counseling sessions and groups (whether in-person or remotely), will be documented for all study participants and entered as covariates in the analyses.

B. Dependent Variables or Outcome Measures

In addition, the study will explore outcomes among participants in the MORE condition relative to treatment as usual (TAU) in regard to opioid use outcomes such as:

- Time until first opioid lapse (primary outcome)
- Opioid abstinence
- Time until MMT dropout
- Total days of methadone treatment
- Total days of opioid or any drug use
- Trajectories of positive and negative affect
- Drug craving
- Pain severity and pain interference

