4.3 Subject Randomization

Since MORE is a closed group, we will randomize cohorts of 10-18 participants (depending on speed of recruitment) at each site to TAU or MORE with block randomization. Once we recruit at least 10 to 18 participants at a particular clinic, we will randomize participants to MORE or TAU, and the MORE group will begin.

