4.5 Number of Subjects

A. Total Number of Subjects

Total number of subjects to be accrued is up to 184.

B. Total Number of Subjects If Multicenter Study

N/A

C. Require Number of Subjects to Complete Research

N/A

E. Feasibility of Recruiting

NBCC serves approximately 500 MMT clients per year, the Lennard Clinic serves approximately 1000 MMT clients at two sites, and JSAS serves about 700. Based on the prior research studies conducted at these clinics and the high amount of clients served, there are no anticipated problems in recruiting ample subjects. Additional sites will be added to the study if necessary if recruitment targets are not being met.

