Exploratory, temporally-dynamic analysis of the effects of mindfulness practice on EMA measures of craving, affect, and pain. Growth curve analyses and multivariate autoregressive latent trajectory analyses (m-ALT) of EMA data will examine antecedents and consequences of drug use as well as the impact of skill practice on craving and drug use. EMA data will yield granular analyses of process variables (mindfulness, reappraisal, and savoring practice) and quantify how skill use dynamically co-varies with pain, craving, and drug use during and after treatment. Lagged growth curve analyses⁴¹ will examine treatment and practice effects on: A) trajectories of positive/negative affect, craving, and pain; B) relationships among these variables over time; and C) how trajectories in affect, craving, and pain predict drug use in separate m-ALT models. The models, like ones published by [name], will estimate cross-lagged and autoregressive effects, as well as latent intercept and growth factors, among EMA variables, conditioned on a treatment group variable and measures of mindfulness, reappraisal, and savoring practice. EMA models will be corrected for multiple comparisons.

AIM 3 Analyses. To test gender as a moderator of treatment response, we will include all main effects and all two-way, and three-way interactions of gender, treatment, and time in GLMM analysis models, and all main effects and the two-way interaction of gender and treatment in the marginal multivariate survival analysis models. A significant gender x treatment x time interaction in GLMM models, tested by F test, indicates that treatment effect on changes in outcomes over time differ by gender. A significant gender x treatment interaction in survival models, tested by Wald test, indicates that treatment effect on time to event differs by gender. In GLMM analysis, gender differences on outcomes at 8, 16, 24, and 52 weeks will be estimated and tested using linear contrasts. Other potential moderators (e.g., race, income, mental health, trauma, and MMT phase) will be explored using similar approaches as exploratory analyses.

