C11. Outcomes and Future Directions. We expect to establish the efficacy of an innovative intervention that can enhance MAT by supporting chronic pain management and MMT adherence while preventing drug use and opioid relapse. Results from this study will inform the development of services in New Jersey and other states seeking efficacious strategies to combat the opioid epidemic. If this study demonstrates MORE's efficacy as an adjunct to MMT, we will follow this study with a Stage IV implementation/dissemination study to enhance the rapidity and fidelity of uptake of the intervention into standard of care for persons with OUD.

B. Provide a power analysis. (As applicable, e.g. quantitative research)

We powered the R33 study based on data from prior research. We used a study of an MBI for substance users,⁴ which showed that the hazard ratio of relapse to drug use for the intervention compared to TAU was 0.46. We thus assumed a similar, but more conservative hazard ratio of relapse to opioid use of MORE compared to TAU at about 0.55. (We are using a slightly more conservative hazard ratio than in the original application due to the increased power obtained by reducing the number of treatment conditions from three to two.) We also assumed that the median relapse time to opioid use is 99 days, based on a prior study of relapse to drug use in a general MMT population.⁵ With 1.5 years of subject accrual and an additional follow-up of 16 weeks after the accrual interval, our study needs 47 subjects per group to test a hazard ratio of 0.55 when comparing MORE to TAU, with 80% power and alpha=5% (two-sided). To account for attrition, we will recruit 85 subjects per group (a total of 184 subjects at a 1:1 ratio for MORE vs. TAU).

Version Number: 15, 2/2/2022 Protocol Number: Pro20190016877

PI Name: [name]
Protocol Title: Mindfulness Oriented
Recovery Enhancement (MORE) as an
Adjunct to Methadone Treatment

RESERVED FOR IRB STAMP DO NOT MODIFY THIS SPACE

C. Describe the steps that will be taken secure the data (e.g., training, authorization of access, password protection, encryption, physical controls, certificates of confidentiality, and separation of identifiers and data) during storage, use, and transmission.

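### The primary survival test clusters on only about 10–18 cohorts and states no small-sample rule; a normal-reference robust Wald test would have about 7–9.7% type I error, not 5%

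*Combined protocol and SAP*

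**What the plan says.** Section 4.3 describes how participants are randomised: "we will randomize cohorts of 10-18 participants (depending on speed of recruitment) at each site to TAU or MORE with block randomization". Section 4.5 caps enrolment: "Total number of subjects to be accrued is up to 184".

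Section 6.1 A, Hypothesis 1.1, analyses time to first opioid lapse and MMT dropout with Kaplan-Meier curves and a marginal model for multivariate survival data. It adds: "Clustering within cohort will be adjusted in the multivariate marginal model analysis". On timing: "Survival analysis will be run once, at 16 weeks post-baseline". No test, reference distribution or finite-cluster correction is given for the MORE–TAU hazard ratio.

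The only test named for these survival models is under the Aim 3 analyses, for a moderator: "A significant gender x treatment interaction in survival models, tested by Wald test". The sensitivity analyses in Section 6.1 A vary how site, cohort and therapist enter the model, but set no reference distribution for the primary test.

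The error rate is fixed in Section 1.5, where the sample size is set "with 80% power and alpha=5% (two-sided"), and again in Section 6.1 B. Section 1.6 A says that usual-treatment characteristics "will be documented for all study participants and entered as covariates in the analyses", so the primary model may also carry covariates.

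**The concern.** A cohort-robust (sandwich) variance is estimated from one summed score contribution per cohort. Its precision depends on the number of cohorts, not the number of people. With 10–18 of them the variance estimate is noisy and biased slightly low, and a normal reference ignores both faults. The Wald test then rejects too often and the confidence interval is too narrow, whether or not outcomes are correlated within cohorts.

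This affects the primary outcome. If the large-sample Wald form is used, a true null is declared significant about 1.4–1.9 times as often as the two-sided 5% on which the trial is powered. If a corrected Wald test or a robust score test is used, the problem does not arise. The plan leaves this open.

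**Working it through.** **The plan's own sample size.** Schoenfeld's formula at hazard ratio 0.55, two-sided 5% and 80% power gives 88 events. With 1.5 years of accrual plus 16 weeks and 99 days taken as the MORE median, the event probability is 0.9245, and 88 / (2 × 0.9245) = 47.6 per group, against the stated 47. With 99 days as the TAU median it is 54.6. The stated figure is therefore a calculation at 5% with no allowance for few clusters.

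**Number of clusters.**
- 184 / 18 = 10.2. Ten cohorts of 18 hold 180 people; all 184 need 11.
- 184 / 10 = 18.4, so at most 18.
- Cross-check from the MORE groups of 5–9 in Section 1.3: 92 / 9 = 10.2 and 92 / 5 = 18.4.

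**Simulation under the null.**
- Median: "We also assumed that the median relapse time to opioid use is 99 days" (Section 6.1 B). Times are taken as exponential with this median in both arms and censored at 16 weeks = 112 days. The event probability is 1 − 2^(−112/99) = 0.543.
- Randomisation is 1:1 within cohort, because the trial is individually randomised.
- The model is a Cox model with variance I⁻¹ M I⁻¹, where M is the sum over cohorts of squared cohort-summed score residuals.
- Each cell has 20,000 runs (Monte Carlo standard error 0.15–0.2 points).
- The covariate runs use four covariates with an assumed log hazard ratio of 0.2 each.

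**Analytic check.** If the statistic behaves like a one-sample t with divisor K instead of K−1, the error is 2 × P(t on K−1 df > 1.96 × √((K−1)/K)).

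Type I error of the robust Wald test against the normal, with no clustering in the data:

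| Cohorts K | MORE + TAU per cohort | No covariates | Four covariates | Analytic |
|---|---|---|---|---|
| 10 | 9+9 | 9.4% | 9.6% | 9.6% |
| 11 | 8+8 or 9+9 | 9.2% | not run | 9.1% |
| 13 | 7+7 | 8.0% | 8.7% | 8.4% |
| 18 | 5+5 | 7.3% | 7.2% | 7.4% |

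With an assumed between-group SD of 0.1–0.3 in the MORE groups' log hazard, the range is 6.8–9.7%. With cohort sizes drawn at random from 10–18 (mean 13.4 cohorts) the error is 8.4%.

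**Other tests, over the same settings.**
- t on K−1 df: 5.3–6.0%.
- t on K−1 df plus the K/(K−1) variance factor: 4.6–5.2%.
- Cohort-robust score test: 4.1–5.0%.
- K/(K−1) factor with a normal reference (no covariates): 6.3–8.2%, so the factor alone is not enough.
- No clustering adjustment (no covariates): 4.8–5.2% at SD 0, 5.1–5.2% at 0.1, 5.4–5.9% at 0.2 and 6.0–7.3% at 0.3. Dropping the adjustment is therefore safe only if the MORE groups differ little.

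**The case against.** The strongest reply is that the plan never commits to a normal-reference Wald test for MORE against TAU. The Wald test is named only for a moderator, no normal reference is stated there, and a Wald statistic can be referred to t. The source cited for the marginal model cannot be consulted here. All of this is true, and it makes the inflation conditional. But the permitted choices run from about 4% to 9.7% error, and the one test named for this model family is the type at risk. The primary test is not fully specified.

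The cluster unit also matters. Only MORE meets as a closed group. With cohort-by-arm clusters (20–36 of them) the error is smaller, about 7.8% down to 6.4%, but still above 5%. With MORE groups as clusters and TAU participants as singletons it is 5.3–6.8%, and t on K−1 df is then conservative (3.2–4.4%). Mixed-arm cohorts are the natural reading of Sections 4.3 and 6.1 A, but the plan should state the unit.

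Ten cohorts would require nearly every cohort to fill to 18, so about 8% is a fairer mid-range figure than 9.7%.

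Finally, Section 6.1 A applies a Bonferroni-Holm adjustment, and Hypothesis 1.1 covers two events; the figures above are for one event at an unadjusted 5%. Holm does not repair p values that are individually too small: at a 2.5% threshold with 10 cohorts the error is 6.1%. The sensitivity analyses with cohort as a fixed or random effect give useful comparisons but leave the primary test undefined.

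**Conclusion.** The concern holds. The primary analysis clusters on about 10–18 cohorts and does not say how the MORE–TAU hazard ratio will be tested. Under the usual large-sample robust Wald test, type I error would be about 7–9.7% instead of 5%, with about 8% typical. This assumes mixed-arm cohorts as clusters, enrolment close to 184, exponential times with a 99-day median and censoring at 112 days. The MORE-group SDs and covariate effects are also assumptions, but the inflation is present without them. The matter should be settled before analysis; it needs no change in design or data collection.

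**What to change.** In Section 6.1 A, Hypothesis 1.1, state that the cluster is the randomised cohort with both arms included. State also that the MORE–TAU hazard ratio is tested by the cohort-robust Wald statistic, with its p value and confidence interval referred to t with K−1 degrees of freedom, K being the number of randomised cohorts. Multiplying the variance by K/(K−1) is optional; t alone leaves 5.3–6.0%, and both together give about 5%. A cohort-robust score test is an acceptable alternative for the p value. Whichever is chosen should be fixed in advance.

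The cost is one sentence and a few lines of code, plus some precision:

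- **Interval width.** The ratio t(K−1)/1.96 is 1.15, 1.14, 1.11 and 1.08 at K = 10, 11, 13 and 18. Multiplied by √(K/(K−1)) it is 1.22, 1.19, 1.16 and 1.11.
- **Power at hazard ratio 0.55**, taking 99 days as the TAU median, with 180–184 people, no attrition and no covariates (10,000 runs per cell):

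| MORE-group SD (assumed) | Normal Wald | t alone | t plus factor | Score test |
|---|---|---|---|---|
| 0 | 76–78% | 69–72% | 65–70% | 64–70% |
| 0.3 | 70–71% | 60–65% | 55–63% | 55–64% |

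The first column is bought partly with inflated error. It is below 80% in any case: with 112 days of follow-up, 92 × (0.543 + 0.350) gives about 82 events, short of the 88 needed.
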